10.3 General Statistical Considerations

Descriptive statistics will be displayed to provide an overview of the study results. For categorical variables, the number and percentage of patients in each category will be presented. The denominator for percentages will be based on the number of patients appropriate for the purpose of analysis. For continuous variables, descriptive statistics will include number of patients (n), mean, standard deviation (SD), median, minimum, and maximum.

In general, Baseline values for efficacy and safety variables will be determined from the last non-missing data collected prior to the first dose of study medication.

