### 2.2. Study Objectives

The primary efficacy objective of the [SYN120-CL03](#) trial is to assess the effect of a fixed dosage of SYN120 on cognition as determined by the Cognitive Drug Research Computerized Cognition Battery (CDR) Continuity of Attention measure in patients with PDD treated with a stable dose of a cholinesterase inhibitor. The key secondary efficacy objective is to assess the effects of SYN120 in this population on CDR Quality of Episodic Memory. Other secondary and exploratory efficacy objectives include the effects of SYN120 on: (a) global impressions of change, (b) other measures of cognition, (c) activities of daily living, (d) nighttime sleep and daytime sleepiness, (e) positive symptoms, and (f) behavioral functioning.

The safety objectives of the [SYN120-CL03](#) trial are to assess the safety and tolerability of a fixed dosage of SYN120 by assessing adverse events (AEs), vital signs (including orthostatic blood pressure measurements), laboratory assessments, electrocardiography (ECG), Unified Parkinson's Disease Rating Scale (UPDRS) Parts I through IV, changes in intensity of symptomatic therapy, and Columbia Suicide Severity Rating Scale (C-SSRS).

The pharmacokinetic objectives of the [SYN120-CL03](#) trial are to estimate population-level pharmacokinetic parameters for plasma levels of SYN120.

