### 3.2.2. Safety Endpoints

The following safety endpoints will be evaluated:

- Proportion of participants experiencing the following and event rates relative to time at risk of: (a) any treatment-emergent AE (TEAE), (b) any severe TEAE, (c) any serious TEAE, (d) any TEAE at least possibly related to study drug, (e) any TEAE leading to permanent study drug discontinuation or early termination from the trial, and (f) any TEAE resulting in death, summarized across all MedDRA terms
- Proportion of participants experiencing and number of unique events of all TEAEs classified by seriousness, severity, relatedness to study drug, action taken with study drug, and outcome, summarized across all MedDRA terms
- Proportion of participants experiencing and number of unique events of each type of TEAE and serious TEAE classified by MedDRA system organ class, high level term, and preferred term
- Proportion of participants experiencing treatment-emergent orthostatic hypotension
- Mean 16-week change from baseline in supine and standing SBP, supine and standing DBP, and differences from supine to standing SBP and DBP
- Mean 16-week change from baseline in weight
- Proportion of participants experiencing treatment-emergent clinically significant laboratory abnormalities classified by assay, whether the abnormality is below or above the normal range, and visit, with cross-classification of frequencies of abnormalities from baseline to each scheduled post-baseline visit at which safety labs are performed
- Mean 16-week change from baseline in laboratory assays
- Proportion of participants experiencing treatment-emergent clinically significant ECG abnormalities
- Mean 16-week change from baseline in ECG parameters
- Mean 16-week change from baseline in UPDRS Part I score, II score, III score, I through III total score, Part IV dyskinesia score, Part IV clinical fluctuations score, Part IV other complications score, and Part IV total score
- Mean 16-week change from baseline in levodopa daily dosage (LDD) and levodopa equivalent daily dosage (LEDD)
- Proportion of participants reporting any treatment-emergent suicidal ideation
- Maximum post-baseline suicidal ideation planning, frequency, duration, controllability, deterrents, and reasons

- Proportion of participants reporting any post-baseline suicidal behavior, actual attempts, non-suicidal self-injurious behavior, interrupted attempts, aborted attempts, preparatory acts or behaviors, or completed suicide

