- Maximum post-baseline suicidal behavior lethality and potential lethality

Reported proportions will use as their denominator all participants in the Safety and Tolerability sample (see [Section 3.5](#) below).

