### **3.5. Analysis Samples**

The following analysis samples will be used for testing safety, tolerability, efficacy, and pharmacokinetic endpoints:

- Safety and Tolerability (ST) Sample: Participants who are eligible, randomized, and take at least one dose of study drug, classified according to the actual treatment received.
- Efficacy Modified Intent-to-treat (mITT) Sample: Participants who are eligible, randomized, have at least one valid pre-treatment and at least one valid post-treatment CDR COA measurement, and take at least one dose of study drug, classified according to their randomized treatment assignment. This sample will include observations made after discontinuation of study drug should any such participants remain on study.
- Efficacy Per-protocol (PP) Sample: Participants who are eligible, randomized, have at least one valid pre-treatment and one valid post-treatment CDR COA measurement, take at least one dose of study drug, and meet all other major protocol compliance criteria specified prior to unblinding, classified according to the actual treatment received. Observations made after permanent discontinuation of study drug (whether due to intolerance, early termination, loss to follow-up, or death) will be omitted, but completion of follow-up on study drug will not be required. Any other individual observations affected by important protocol deviations may also be excluded, as specified prior to unblinding.
- Pharmacokinetic (PK) Sample: Participants in the ST sample who have at least one valid determination of their plasma SYN120 concentration.

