### **3.9.3. Safety Labs**

The absolute level and the absolute change from baseline for each safety laboratory assay will be summarized as means, standard deviations, medians, and ranges at each visit by treatment group. The proportion of participants with safety lab levels below the lower limit of normal or above the upper limit of normal will be summarized by treatment group by visit and at any post-baseline visit. Shift tables will be used to summarize changes in laboratory assays from baseline to the week 4, 8, and 16 visits when classified as below the lower limit of normal, within normal limits, and above the upper limit of normal separately by treatment group.

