### **3.9.4. Vital Signs**

The absolute level and the absolute change from baseline for vital signs will be summarized as means, standard deviations, medians, and ranges at each visit by treatment group.

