### **3.9.5. Blood Pressure**

The absolute level and the absolute change from baseline of supine and standing SBP, supine and standing DBP, and differences from supine to standing SBP and DBP will be summarized as means, standard deviations, medians, and ranges at each visit by treatment group. The proportion of participants who experience orthostatic hypotension (as defined in [Section 3.3.11](#)) at the week 4, 8, and 16 visits and at any post-baseline visit will be summarized by treatment group.

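### The all-ST denominator in SAP 3.2.2, applied to by-visit laboratory and orthostatic hypotension proportions, counts unassessed patients as not abnormal and understates each rate by the unmeasured share

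*SAP*

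**What the plan says.** SAP 3.2.2 lists the safety endpoints and then states: "Reported proportions will use as their denominator all participants in the Safety and Tolerability sample". One endpoint in that list is reported by visit. It is the proportion with treatment-emergent, clinically significant laboratory abnormalities, "classified by assay, whether the abnormality is below or above the normal range, and visit".

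Two later sections also plan by-visit proportions and name no other denominator. In SAP 3.9.3 the proportions below and above the laboratory normal range "will be summarized by treatment group by visit and at any post-baseline visit". In SAP 3.9.5 the proportion with orthostatic hypotension "at the week 4, 8, and 16 visits and at any post-baseline visit will be summarized by treatment group".

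SAP 3.5 defines the ST sample as "Participants who are eligible, randomized, and take at least one dose of study drug, classified according to the actual treatment received". It asks for no assessment after baseline.

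Protocol 10.3 is more flexible: "The denominator for percentages will be based on the number of patients appropriate for the purpose of analysis". However, the SAP introduction gives the SAP precedence on analysis where the two documents differ.

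The SAP has no missing-data rule for these proportions. SAP 3.8.6 deals with efficacy. The rule in SAP 3.8.1 that moves Early Termination data forward to the following planned visit belongs to the primary efficacy model.

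**The concern.** A by-visit rate is normally read as the share of patients examined at that visit who were abnormal. Under this rule it is the share of everyone ever dosed who was both examined and found abnormal. Patients who have left, or who missed the visit, are in effect scored as normal. The shortfall grows as fewer patients are measured, and it differs between arms if loss differs.

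The stakes are not trivial. The protocol synopsis singles out orthostatic hypotension among the vital signs. Protocol 10.7 itself foresees that withdrawal could be higher on SYN120, and plans for this on the efficacy side only. The means in SAP 3.9.3 and 3.9.5 can use only measured patients, so neighbouring rows of one table would rest on different numbers of patients.

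**Working it through.** **Inputs from the documents**
- 80 randomized 1:1, so 40 per arm (SAP 2.4 and 3.4; Protocol 10.8).
- Loss to follow-up of up to 15% (SAP 3.4).
- Effect size 0.69, two-sided alpha 0.05, power at least 80% (SAP 3.4), sized on a two-sample t-test (Protocol 10.8).

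**Assumptions**
- All 40 per arm enter the ST sample.
- The share without a safety assessment at Week 16 equals the planned loss.
- True abnormality rates are 10%, 20% or 30%, constant over time.
- Loss at Weeks 4 and 8, and any split of loss between arms, is assumed. The documents give only the 15% ceiling.

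**1. The plan's own figure.** The documents state no figure for safety proportions. The one stated figure that uses the loss assumption is the power. With 40 × 0.85 = 34 measured per arm, a two-sided t-test at effect size 0.69 has 80.05% power, which agrees with the stated minimum of 80%. In reverse, the test needs 34 per arm, and 34 / 0.85 = 40. So the plan works with 34 of 40 measured at Week 16.

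**2. Formula.** Let N be the arm's ST count, m the number assessed at the visit, and p the rate among those assessed. An unassessed patient cannot be counted as abnormal, so

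reported rate = (p × m) / N = p × (m / N).

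**3. Equal loss.** At Week 16, m / N = 34 / 40 = 0.85. For p = 20% the expected count is 0.20 × 34 = 6.8, and 6.8 / 40 = 17%. With assumed cumulative loss of 5%, 10% and 15%:

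| True rate | Week 4 (38 of 40) | Week 8 (36 of 40) | Week 16 (34 of 40) |
|---|---|---|---|
| 10% | 9.5% | 9.0% | 8.5% |
| 20% | 19.0% | 18.0% | 17.0% |
| 30% | 28.5% | 27.0% | 25.5% |

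**4. Unequal loss at Week 16, averaging 15%, true rate 20% in both arms.** The splits are assumed.

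| Loss, SYN120 vs placebo | Reported, SYN120 vs placebo | Spurious difference |
|---|---|---|
| 20% vs 10% | 0.20 × 0.80 = 16% vs 0.20 × 0.90 = 18% | −2 points |
| 25% vs 5% | 15% vs 19% | −4 points |
| 30% vs 0% | 14% vs 20% | −6 points |

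**5. A true excess of 30% vs 20%.** With loss of 20% vs 10%, the report is 24% vs 18%, so 10 points become 6. With loss of 25% vs 5%, it is 22.5% vs 19.0%, or 3.5 points.

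**6. Check of the remedy.** With those assessed as denominator, 6.8 / 34 = 20% at any level of loss. This equals the true rate only if unassessed patients have the same rate. Suppose 15% are unassessed and their rate is 30% against 20% in the rest. The true rate is then 0.85 × 20% + 0.15 × 30% = 21.5%. The assessed denominator gives 20% and the ST denominator 17%. The ST denominator is exact only if no unassessed patient is abnormal.

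**The case against.** **The sentence may only name the analysis sample.** It points to the sample definitions in SAP 3.5, and SAP 3.9.3 and 3.9.5 do not repeat it, so Protocol 10.3 could still govern by-visit percentages. This has some force for SAP 3.9.5, where applying the rule is an inference. It has less for laboratory results, because the sentence specifies a denominator and a by-visit laboratory proportion stands in the same list.

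**The reach is limited.** This stands. The SAP objective counts orthostatic pressure as a vital sign ("vital signs (including orthostatic blood pressure measurements"), but orthostatic hypotension is the only vital-sign proportion planned by visit. SAP 3.9.4 plans only continuous summaries: "The absolute level and the absolute change from baseline for vital signs will be summarized as means". For TEAEs and any-time endpoints an all-ST denominator is conventional. Shift tables are described as frequencies, so no defect is shown there unless percentages are added.

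**A reader might infer that the rule hides SYN120's own safety signal.** The documents do not support that.
- Patients who stop study drug are to stay on the normal schedule (SAP 2.4), so intolerance alone does not remove them from measurement.
- Patients who leave are asked to attend an Early Termination visit with laboratory tests and blood pressure (Protocol 6.2.10), which can feed the any-post-baseline proportions.
- Clinically significant laboratory findings are also recorded as AEs (Protocol 10.5.1), and SAP 3.2.2 reports TEAE rates per time at risk.
- Time to drug discontinuation is compared by log-rank test (SAP 3.10.2).
- The largest distortions above rest on assumed splits of loss.

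**The numbers are small and partly recoverable.** At equal 15% loss the shortfall at a true 20% is 8.0 − 6.8 = 1.2 patients of 40, against a standard error of √(0.2 × 0.8 / 40) = 6.3 points per arm. SAP 3.9.3 and 3.9.5 plan no test of these proportions. SAP 3.1.2 includes the number of subjects in continuous summaries, so a careful reader could recompute the rate. All this stands, but it does not justify printing a wrong percentage.

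**Conclusion.** The concern holds for by-visit laboratory proportions and, by the rule's unqualified wording, for by-visit orthostatic hypotension. Followed as written, SAP 3.2.2 treats patients not assessed at a visit as not abnormal.

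The relative understatement equals the unmeasured share: 15% at the planned ceiling, so 20% is shown as 17% at Week 16. Between arms there is no spurious difference when loss and true rates are equal. At a true 20% in both arms, the assumed splits give 2 to 6 points in favour of the arm with more loss.

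Three stronger statements should not be made. That reported rates fall with time holds only if the true rate is roughly constant; a rising rate can still rise on paper. That all safety proportions are affected is wrong, because TEAE and any-time proportions are conventional as planned. That a SYN120 signal would be hidden depends on unequal loss that the documents do not quantify, and overlooks the other safety outputs.

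**What to change.** Amend SAP 3.2.2, with matching text in 3.9.3 and 3.9.5, before unblinding:
- Keep all ST participants as the denominator for TEAE and any-time (any post-baseline) proportions.
- For by-visit laboratory and orthostatic hypotension proportions, use ST participants with a non-missing assessment at that visit. Where shift tables show percentages, also require a baseline value.
- Print the numbers assessed and missing for each arm and visit.
- State how Early Termination safety data are assigned to visits.

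The cost is SAP wording and table shells; no new data or change of sample size is needed. The drawbacks are that denominators will vary between tables, and that the by-visit rate is unbiased only if missingness is unrelated to the abnormality. That is why the numbers missing must be shown.

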### 3.2.3. Tolerability Endpoint

Participants will be judged tolerant of study drug if they complete their week 16 visit without prior permanent discontinuation of study drug and without prior study drug suspension lasting longer than 14 days. Tolerability will be summarized as the proportion of participants in a treatment group who are tolerant of study drug.

## 3.3. Measurement Definitions

### 3.3.1. CDR Measures

The CDR ([Wesnes et al. 1992](#)) is a computerized neuropsychological test battery to assess cognitive tasks based on measures of choice reaction time, vigilance, and the sensitivity and speed of digit, word and picture recognition. The stimuli are presented on a computer screen and the subjects respond by pressing either a “Yes” or “No” on a response box. Detailed of the assessments are described in the clinical protocol.

Continuity of Attention (COA) measures the ability to sustain attention and avoid error. COA is calculated as  $(VIGACC*0.45) + (CRTACC*0.5) - VIGFA$ , where VIGACC is digit vigilance accuracy, CRTACC is choice reaction time accuracy, and VIGFA is digit vigilance false alarms. Higher COA scores represent greater sustained attention and avoidance of errors.

Quality of Episodic Memory (QEM) measures the ability to store, hold, and retrieve information of an episodic nature. QEM is calculated as  $(DRECOACC + DRECNACC - 100) + (DPICOACC + DPICNACC - 100) + ((IRCL - IRCLERR)*100 / 12) + ((DRCL - DRCLERR)*100 / 12)$ , where DRECOACC is word recognition original stimuli accuracy, DRECNACC is word recognition new stimuli accuracy, DPICOACC is picture recognition original stimuli accuracy, DPICNACC is picture recognition new stimuli accuracy, IRCL is immediate word recall words recalled, IRCLERR is immediate word recall errors, DRCL is delayed word recall words recalled, and DRCLERR is delayed word recall errors. Higher QEM scores represent greater ability to store, hold, and retrieve information of an episodic nature.

Quality of Working Memory (QWM) measures the ability to store and retrieve information in working memory. QWM is calculated as SPMSI + NWMSI, where SPMSI is the sensitivity index for spatial working memory and NWMSI is the sensitivity index for numeric working memory. Sensitivity index ([Frey and Collier 1973](#)) measures the ability to identify previously presented stimuli and reject stimuli which were not previously presented. A score of 1 represents perfect discrimination; all of the previously presented stimuli are correctly identified and all distractor stimuli are correctly rejected as being novel. A score of -1 represents perfect reverse discrimination; none of the previously presented stimuli are correctly identified, and all distractor stimuli are selected as being novel. A score of 0 represents chance performance with no

discrimination between previously presented stimuli and distractor stimuli. Sensitivity index is calculated as  $(\text{HIT} - \text{FA}) / (2(\text{HIT} + \text{FA}) - (\text{HIT} + \text{FA})^2)$ , where HIT is the proportion of previously presented items that were correctly identified and FA is the proportion of novel items that were incorrectly identified. If both HIT and FA are 0 or both HIT and FA are 1, leading to an indeterminant ratio as calculated above, then the sensitivity index is assigned a value of zero. Higher QWM scores represent greater ability to store and retrieve information in working memory.

Power of Attention (POA) measures the intensity of concentration at a particular moment. POA is calculated as SRTM + VIGRT + CRTM, where SRTM is median simple reaction time, VIGRT is mean digit vigilance reaction time, and CRTM is median choice reaction time. Higher POA scores represent less intensity of concentration at a particular moment.

Speed of Memory Retrieval (SMR) measures the time it takes to retrieve a memory. SMR is calculated as SPMRTM + NWMRTM + DRECRTM + DPICRTM, where SPMRTM is median spatial working memory reaction time, NWMRTM is median numeric working memory reaction time, DRECRTM is median word recognition reaction time, and DPICRTM is median picture recognition reaction time. Higher SMR scores represent slower speed in retrieving memories.

Immediate Word Recall is measured by the CDR variables IRCL (number of words correctly recalled) and IRCLERR (number of words recalled that were not presented during current testing session).

Simple Reaction Time is measured by the CDR variable SRTM (median speed of individual correct responses).

Digit Vigilance is measured by the CDR variables VIGRT (mean speed of individual responses to targets within 1.5 sec window), VIGACC (percentage of targets responded to within 1.5 sec window), and VIGFA (number of responses falling outside of 1.5 sec window).

Choice Reaction Time is measured by the CDR variables CRTM (median speed of individual correct responses) and CRTACC (percentage of stimuli correctly identified).

Numeric Working Memory is measured by the CDR variables NWMRTM (median speed of individual correct responses to all stimuli) and NWMSI (Frey and Colliver sensitivity index).

Spatial Working Memory is measured by the CDR variables SPMRTM (median speed of individual correct responses to all stimuli) and SPMSI (Frey and Colliver sensitivity index).

Delayed Word Recall is measured by the CDR variables DRCL (number of words correctly recalled) and DRCLERR (number of words recalled that were not presented during current testing session).

Word Recognition is measured by the CDR variables DRECRTM (median speed of individual correct responses to all stimuli), DRECOACC (percentage of original stimuli correctly identified), and DRECNACC (percentage of novel stimuli correctly identified).

Picture Recognition is measured by the CDR variables DPICRTM (median speed of individual correct responses to all stimuli), DPICOACC (percentage of original stimuli correctly identified), and DPICNACC (percentage of novel stimuli correctly identified).

### 3.3.2. CDR Datasets

Two datasets will be obtained from Bracket: (1) raw data, and (2) adjudicated data. The adjudicated dataset, with modifications suggested by [name] that in his expert opinion would best reflect the cognitive status of participants at the time of testing, will be used for primary analysis. All changes from the raw data resulting from algorithmic flipping of data and from [name] adjudication will be documented together with their justification.

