5.10 Blinding

The randomization schedule will be produced by an unblinded statistician who is otherwise not involved with the study team, Steering Committee, or Sponsor. The randomization schedule will use permuted blocks, stratified by site. The IMP vendor will generate unblinding **scratch-off labels** for patients' randomization assignments based on the randomization schedule produced by the unblinded statistician. The randomization schedule and unblinding **scratch-off labels** will be kept strictly confidential until the time of unblinding and should not be **scratched off** without authorization. Blinding will not be compromised for individuals involved with operational aspects of the study or individuals involved with the planning and conduct of the final statistical analyses, including an independent statistician. **Scratch-off labels should be removed from the kit and adhered in the patient's source document.**

The identity of the dosing group assignments will be concealed by identical appearance, packaging, labeling, and schedule of administration.

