### **2.6. Allocation Concealment**

The randomization schedule is known only by the unblinded study statistician who generated the schedule and by the study drug distributor and the sponsor's quality control and bioanalytical staff and subcontractors as specified in the [SYN120-CL03](#) Study Randomization Specification. Concealment of the true treatment allocation of specific participants is achieved by use of anonymous subject identifiers to link participants with specific study drug kits and by use of matching active and placebo tablets and titration schedules. Members of the SYNAPSE Steering Committee, site investigators and other site staff, clinical coordination and data management staff, the blinded study statistician, the medical monitor, and all participants are blinded to participant treatment allocations. The Safety Data Monitor (SDM) and members of the SDM Advisory Group are provided treatment-specific information in order to monitor the trial but

such information is masked by use of coded values to identify the treatment groups. The SDM may request the true treatment identities.

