## 3.8. Efficacy Analysis

### 3.8.1. Primary Analysis of the Primary Efficacy Endpoint

The primary efficacy analysis will be performed on the mITT sample using the adjudicated CDR data and will use a shared-baseline, repeated-measures analysis of variance that includes fixed effects for visit (3 levels: Baseline, Week 8, and Week 16) and the interaction between treatment group (2 levels: SYN120 and placebo) and post-baseline visit (2 levels: Weeks 8 and 16), random center-specific intercepts, and unstructured within-person covariance. The interaction between treatment group and visit will be restricted to post-baseline visits by including a numeric indicator variable (0 pre-treatment, 1 post-treatment) in the interaction. Use of a shared baseline reflects the true state of the population sampled prior to randomization and has the advantage of adjusting for any chance differences at baseline in a manner similar to analysis of covariance ([Liang and Zeger, 2000](#)) with potentially greater efficiency with more than one follow-up visit and drop-out. Data from Early Termination visits will be assigned to the next scheduled post-baseline visit. The following SAS code specifies the model:

```
proc mixed data=xxx method=reml;
  class site id trtrnd visit;
  model Value = visit post*trtrnd*visit;
  random intercept / subject=site type=vc;
  repeated visit / subject=id(site) type=un;
```

Treatment-dependent differences in the change from baseline to the week 16 visit on the CDR COA will be estimated by a linear contrast and tested using a two-tailed Wald-test at alpha = 0.05. The following SAS code specifies the linear contrasts used to estimate treatment- and visit-specific means, treatment- and visit-specific changes from baseline, and treatment-dependent visit-specific changes from baseline (with the sort order for treatment group being SYN120 first and placebo second):

```
estimate "0|Active |Wk  00" intercept 1 visit  1 0 0 post*trtrnd*visit 0 0 0  0 0 0 / cl;
estimate "0|Active |Wk  08" intercept 1 visit  0 1 0 post*trtrnd*visit 0 1 0  0 0 0 / cl;
estimate "0|Active |Wk  16" intercept 1 visit  0 0 1 post*trtrnd*visit 0 0 1  0 0 0 / cl;
estimate "1|Active |dWk 08" intercept 0 visit -1 1 0 post*trtrnd*visit 0 1 0  0 0 0 / cl;
estimate "1|Active |dWk 16" intercept 0 visit -1 0 1 post*trtrnd*visit 0 0 1  0 0 0 / cl;
estimate "0|Placebo|Wk  00" intercept 1 visit  1 0 0 post*trtrnd*visit 0 0 0  0 0 0 / cl;

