### 3.8.2. Secondary Analyses of the Primary Efficacy Endpoint

Several secondary analyses will be investigated to assess sensitivity of our estimates of treatment effect to alternative modeling assumptions and alternative handling of the CDR data.

- Random-slopes model: The repeated-measures covariance will be replaced with random participant-level intercepts and slopes with unstructured covariance. Data from Early Termination visits will be placed at their observed follow-up time. The following SAS code

specifies the model and the linear contrasts used to estimate treatment-specific and treatment-dependent changes over 16 weeks:

```
proc mixed data=xxx method=reml;
  class site id trtrnd;
  model Value = week trtrnd*week;
  random intercept / subject=site type=vc;
  random intercept week / subject=id(site) type=un;
  estimate "1|Active |Chg 16" intercept 0 week 16 trtrnd*week 16 0 / cl;
  estimate "1|Placebo|Chg 16" intercept 0 week 16 trtrnd*week 0 16 / cl;
  estimate "2|ActvPbl|Chg 16" intercept 0 week 0 trtrnd*week 16 -16 / cl;
```

- Shared-baseline, repeated-measures ANOVA model with pMI for missing data: The shared-baseline repeated-measures ANOVA model described above for the primary analysis will be applied to datasets generated by placebo multiple imputation (Ayele et al. 2014). Fifty imputed datasets will be generated for a given endpoint.
- Cochran-Mantel-Haenszel row mean score LOCF: 16-week change scores will be compared by mean score test using modified ridit scores stratified by clinical site. The last observed CDR COA value will be carried forward when CDR COA values are not available from the Week 16 visit. The following SAS code specifies the model:

```
proc freq data=xxx;
  table site * trtrnd* Value / cmh scores=modridit;
```

- Cochran-Mantel-Haenszel row mean score WO: 16-week change scores will be compared by mean score test using modified ridit scores stratified by clinical site. The worst observed CDR COA 16-week change from baseline will be imputed when CDR COA values are not available from the Week 16 visit.
- PP sample: The primary efficacy model and the secondary random-slopes model will be applied to the PP sample.
- Alternative CDR data: The primary efficacy model and the secondary random-slopes model will be applied to mITT and PP samples using the raw CDR data.

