### 3.8.3. Secondary Efficacy Endpoints

The key secondary efficacy endpoint will all be analyzed using the same analysis samples and models as specified for the primary efficacy endpoint in [Sections 3.8.1](#) and [3.8.2](#). Non-key secondary efficacy endpoints and exploratory efficacy endpoints will all be analyzed using the mITT sample and the primary efficacy analysis described in [Section 3.8.1](#). Variables that are strictly positive and strongly right-skewed (e.g., CDR POA, CDR SWM, and other CDR measures of reaction time) will be analyzed on their original scale and after log-transformation. Estimates from analysis of log-transformed data will be back-transformed for reporting.

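### Do expert-adjudicated CDR scores, with no stated edit rules or lock date, leave the mITT sample and the primary result open?

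*SAP*

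**What the plan says.** SAP 3.3.2 describes two CDR files, raw and adjudicated. The adjudicated one carries an expert's modifications which "in his expert opinion would best reflect the cognitive status of participants at the time of testing, will be used for primary analysis". The same section requires every departure from the raw file to be documented and justified, whether it comes from the flipping algorithm or from the expert. SAP 3.8.1 repeats the choice: "The primary efficacy analysis will be performed on the mITT sample using the adjudicated CDR data".

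To enter mITT under SAP 3.5, a participant must "have at least one valid pre-treatment and at least one valid post-treatment CDR COA measurement". Protocol 10.1 uses the same idea. Neither document defines *valid*. For the per-protocol sample, participants must also "meet all other major protocol compliance criteria specified prior to unblinding", and SAP 3.11 sets the same timing for important deviations. No such timing is written for the adjudicated file or for the mITT judgement.

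On concealment, SAP 2.6 begins "The randomization schedule is known only by the unblinded study statistician who generated the schedule" and then adds the drug distributor and the sponsor's quality control and bioanalytical staff and subcontractors. Protocol 5.10 says the schedule and unblinding labels "will be kept strictly confidential until the time of unblinding". As a check on adjudication, SAP 3.8.2 plans this: "The primary efficacy model and the secondary random-slopes model will be applied to mITT and PP samples using the raw CDR data". SAP 3.8.3 gives the key secondary endpoint the same set of analyses.

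**The concern.** The primary endpoint is a computed score, and here one person's judgement may alter it before analysis. If that judgement can also void a session, it decides which records are missing. If it voids a participant's only baseline session or all post-baseline sessions, it may decide who is in mITT. The screening CDR sessions are training only (Protocol 7.1), so Visit 2 is the single evaluable baseline.

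The planned check seems to have holes. The raw-data rerun is on the mITT and PP samples, and the SAP does not say which file defines membership for it. It covers two of five models; placebo imputation, LOCF and worst-outcome are left out. The other secondary CDR composites have no raw rerun, since "Non-key secondary efficacy endpoints and exploratory efficacy endpoints will all be analyzed using the mITT sample and the primary efficacy analysis described in" SAP 3.8.1 alone.

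Two analysts could therefore build different mITT samples. There is also a possible bias. The diagnostic criteria in Protocol 14.2 describe attention in Parkinson's disease dementia as fluctuating, so a poor session may be disease and not artefact. Voiding poor sessions, even blind, would remove more placebo than SYN120 records if the drug works.

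**Working it through.** **1. The plan's own power.** Inputs: 80 randomized 1:1, 15% loss, effect 0.69 SD, two-sided alpha 0.05, two-sample t-test (Protocol 10.8, SAP 3.4). Evaluable per arm: 40 × 0.85 = 34. Noncentrality = 0.69 × √(34/2) = 2.845 on 66 degrees of freedom, giving power 80.05%. The stated figure of at least 80% reproduces.

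**2. What adjudication is said to do.** SAP 3.3.2 speaks of modifications meant to reflect cognitive status and of algorithmic flipping. This reads as re-scoring. Voiding is neither mentioned nor excluded, so everything below is conditional on it.

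**3. Arm-blind voiding of the worst sessions.** The voiding rate is not in the documents; 0–10% is assumed. Treat 16-week changes as N(0.69, 1) on SYN120 and N(0, 1) on placebo, and remove the lowest pooled share x. The cut c solves ½Φ(c) + ½Φ(c − 0.69) = x. The remaining difference is 0.69 + φ(c − 0.69)/[1 − Φ(c − 0.69)] − φ(c)/[1 − Φ(c)].

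| x | c | Voided, placebo | Voided, SYN120 | Difference left (SD) |
|---|---|---|---|---|
| 3% | −1.643 | 5.0% | 1.0% | 0.608 |
| 5% | −1.395 | 8.1% | 1.9% | 0.572 |
| 10% | −1.012 | 15.6% | 4.4% | 0.505 |

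A complete-case t-test on 34 per arm (20,000 simulated trials), voiding the lowest 0, 2, 3 or 7 of 68, gives power 80%, 74%, 72% and 62%, with type I error 4.8–5.1%.

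**4. The same scenario with Week 8 used.** A complete-case t-test is not the planned analysis. SAP 3.8.1 fits baseline, Week 8 and Week 16 together. An approximation without the site effect regresses Week 8 on baseline and arm (arm effect a₁), then observed Week 16 on baseline, Week 8 and arm (Week 8 slope b, arm effect a₂). The Week 16 effect is a₂ + b·a₁. Assumptions: 34 per arm, equal visit correlation 0.5 or 0.7, Week 8 effect 50% or 100% of Week 16, SD of change 1, voiding the lowest changes or the lowest scores.

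| Voided of 68 | Estimate (SD) | Power |
|---|---|---|
| 0 | about 0.69 | about 85–90% |
| 2 | 0.63–0.66 | about 80–88% |
| 7 | 0.55–0.60 | about 73–82% |

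The power ranges allow for a few points' difference between ways of computing the standard error. Attenuation remains, but power is well above the complete-case figures.

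**5. Would the raw rerun show it?** In steps 3 and 4 the participant loses Week 16 but keeps Week 8. One post-baseline score is enough for mITT, whichever file defines membership. The raw rerun then restores the Week 16 score, and the raw and adjudicated estimates sit side by side.

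**6. The case that could escape.** This needs every post-baseline session voided, or the single baseline session. For the first, restoring the participant hardly moves the adjudicated primary estimate. With a shared baseline, the fitted Week 16 mean in an arm is approximately Ȳ₁₆ + b(μ̂₀ − Ȳ₀), with averages over participants who have follow-up. A baseline-only record enters through μ̂₀. The difference between arms is (Ȳ₁₆,A − Ȳ₁₆,P) − b(Ȳ₀,A − Ȳ₀,P), so μ̂₀ cancels, apart from small effects through the estimated covariance and site terms.

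**7. Blinding.** The list in SAP 2.6 is closed and the CDR adjudicator is not on it. SAP 3.8.7 sends by-treatment summaries to a person whose name is removed. Even if this is the adjudicator, the primary estimates in those summaries are computed from the adjudicated file, so that file must exist first.

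**The case for a change.** The best case for amending is that the text really is silent and the remedy is cheap. The SAP writes the pre-unblinding condition for PP criteria and for important deviations, yet not for the file and sample behind the primary test. SAP 2.6 names the blinded roles and leaves the adjudicator out. *Valid* is undefined, and Protocol 10.7 puts participants who discontinue or withdraw in mITT after one dose without mentioning validity, although SAP Section 1 gives the SAP precedence on analysis. The imputation-type analyses, which turn on what counts as missing, have no raw counterpart. A few sentences would settle all of this.

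The omissions stand as facts. They do not show that the analysis as written goes wrong. Defining validity from the raw file would bring back participants who add almost nothing to the adjudicated primary model. In the worst-outcome analysis it would also assign them the worst observed change, which is a consequence to weigh and not a clear gain. Raw reruns of LOCF and worst-outcome, or of Power of Attention and Speed of Memory Retrieval, would be extra sensitivity work. The non-key endpoints get no PP, placebo-imputation or LOCF runs either, so the lack of a raw rerun is in line with their rank.

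**Conclusion.** No change to the plan is needed. This is a gap in detail that a blinded analyst would fill in the ordinary way: treat a COA score as valid when its components are recorded and usable, finish the adjudicated file before the blind is broken, and derive the raw-data sample from the raw file. The written plan already keeps the schedule from the adjudicator, requires each edit to be justified, and tests the choice of file on the primary and key secondary endpoints.

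The size of the risk is conditional. If 2–7 of 68 Week 16 sessions were voided, worst first and blind to arm, the effect would shrink from 0.69 to roughly 0.55–0.66 SD. That error runs against the drug, leaves type I error near 5%, and shows up in the raw rerun. The complete-case power figures of 62–74% should not be used as its size, because they ignore Week 8 and do not measure the mITT question.

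The conclusion rests on reading SAP 2.6 as covering the adjudicator. Evidence that adjudication was done with knowledge of arm, or reopened after unblinding, would change it; nothing in the documents suggests either.
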